6.7.7 Reactions Occurring During the Maintenance Period

This phase consists of the subject receiving the 300 mg/d dose of study product for approximately 24 weeks. For any noted symptoms during the Maintenance Period, the same study product dosing guidelines and procedures will be followed as for the Up-dosing Period.

6.8 Missed Peanut OIT (Study Product) Doses during Up-dosing:

Missed doses of study product at any phase of the study can pose a significant risk to the enrolled subjects, but the risk is believed to be highest during the Up-dosing Period. The algorithm for missed consecutive doses of study product is as follows:

- Miss 1 dose The next dose would be at the current dose level and could be given at home
- Miss 2 doses in a row The next dose would be the current dose level and could be given at home
- Miss 3 doses in a row The next dose would be the current dose and would be given under supervision in the CRC
- Miss 4 doses in a row The next dose would be the current dose and would be given under supervision in the CRC
- Miss 5-7 doses in a row Initiate the next dose at approximately 50% of the last tolerated dose (to the nearest feasible available whole dose that is ≤50% of the last tolerated dose). This dose is to be administered under supervision in the CRC. If tolerated, dose escalation may resume with dose increases of 1 dose level occurring no more frequently than weekly and generally no less frequently than every 4 weeks until the subject has returned to the dose level at which the lapse in dosing occurred. If symptoms occur, the dosing guidelines for the up-dosing period apply.
- Missing > 7 consecutive days of dosing due to non-compliance, ie, for any reason other than treatment of an AE or a study product dispensing error, constitutes an individual stopping rule and the subject is to stop taking study product. The subject will be considered an escalation failure nonresponder, and will be asked to return to the CRC 14 days following their last dose of study product to undergo an Early Discontinuation Visit (Section 6.5).
- Additionally, excessive missed dosing, defined as 3 consecutive days of missed doses on 3 occasions during the Up-dosing Period or on 3 occasions during the Maintenance Period, for any reason other than treatment of an AE, constitutes an individual stopping rule and the subject is to stop taking study product. The subject will be considered an escalation failure nonresponder, and will be asked to return to the CRC 14 days following their last dose of study product to undergo an Early Discontinuation Visit (Section 6.5).
- If study product has been withheld for 8 to 14 consecutive days as treatment for an AE or due to a study product dispensing error, dosing may be reinitiated at approximately 25% of the last tolerated dose (to the nearest feasible available whole dose that is ≤ 25% of the last tolerated dose) if the lapse in dosing occurred during the Up-dosing Period. If the lapse in dosing occurred during the Maintenance Period, dosing may, at the investigator's discretion, be reinitiated at 50% of the last tolerated dose (to the nearest feasible available)

whole dose that is \leq 50% of the last tolerated dose). The reduced dose is to be administered under supervision in the CRC. If tolerated, dose escalation may resume with dose increases of 1 dose level occurring no more frequently than weekly and no less frequently than every 4 weeks until the subject has returned to the dose level at which the lapse in dosing occurred. If symptoms occur, the dosing guidelines for the Up-dosing period apply.

If study product has been withheld for ≥ 15 consecutive days for any reason, at any point in the study (with the exception of a dosing hiatus instituted for chronic/recurrent GI AEs at or before the 20 mg dose level, as per Section 6.7.3.2), the subject will be considered an escalation failure nonresponder, and will be asked to return to the CRC 14 days following their last dose of study product to undergo an Early Discontinuation Visit (Section 6.5).

No attempt should be made to make up for a missed dose if greater than 6 hours have elapsed since usual time of dosing.

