4.3.1 Criteria

No subject randomized into this trial who discontinues treatment for any reason will be replaced.

Unless required for safety reasons (ie, medical treatment of SAEs), subjects eligible for an Exit DBPCFC will not be unblinded earlier than their scheduled DBPCFC. Subjects who are considered escalation failures will be unblinded no sooner than Week 64 (or when the last subject completes the Exit DBPCFC).

Any subject will be prematurely terminated from additional allergen exposures for the following reasons:

- 1. Life-threatening symptoms (CoFAR Grade 4; refer to **Table A4** in **Appendix 4**), including, but not limited to, anaphylaxis resulting in hypotension, neurological compromise, or mechanical ventilation secondary to peanut OIT dosing or any peanut food challenge
- 2. Severe symptoms (CoFAR Grade 3; refer to **Table A4** in **Appendix 4**), including, but not limited to, those that require intensive therapy (to be determined by the investigator, but may include such interventions as IV epinephrine, intubation, or admission to an intensive care unit) or those that are recurrent

Any subject may be prematurely terminated from additional allergen exposures for the following reasons:

3. Poor control or persistent activation of secondary atopic disease (eg, atopic dermatitis, asthma)

- 4. Started on angiotensin receptor blockers (ARBs), angiotensin-converting enzyme (ACE) inhibitors, beta-blockers, or other prohibited medications, with no alternative medications available per the prescribing doctor
- 5. Pregnancy
- Non-adherence (non-compliance) with home peanut OIT (study product) dosing, as indicated by missing > 7 consecutive days on any 1 occasion, or 3 consecutive days on 3 or more occasions during the Up-dosing Period, as this could constitute a potential safety issue
- 7. Medically indicated circumstances (eg, as part of the treatment for intercurrent adverse events) that require missed peanut OIT (study product) dosing for >14 consecutive days

Any subject may also be prematurely terminated from the study if:

- 8. The subject elects to withdraw consent from all future study activities, including follow-up
- 9. The subject is "lost to follow-up" (ie, no further follow-up is possible because attempts to reestablish contact with the subject have failed)
- 10. The subject develops biopsy-documented eosinophilic esophagitis (EoE)

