7.10.2 Individual Stopping Rules

Individuals may stop the study at any time if they experience subjectively intolerable adverse events or dosing symptoms. They must halt up-dosing and re-start with a reduced dose if more than 3 days of dosing are missed. Seven or more consecutive days of missed dosing due to non-compliance constitutes an individual stopping rule, as does a significant number of episodes of missed dosing (ie, 3 or more consecutive days on at least 3 occasions) during the Up-dosing Period. Missing 15 or more consecutive days of dosing for any reason also constitutes an individual stopping rules, the reader is referred back to Section 4.3.1.

Occurrence of any of the following will result in the cessation of dosing and the subject being discontinued from the study as an escalation failure nonresponder:

- Failure to accomplish up-dosing of study product after 3 attempts
- Failure to identify a tolerated dose of study product after 3 attempts at dose reduction
- Administration of 3 or more doses of epinephrine for the treatment of any dose-related allergic reaction.

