#### 7.4.2. Classification as a non-responder

If a subject cannot be classified as a responder, then that subject should be classified as a non-responder. If a subject meets any of the following conditions, then the subject is a non-responder:

- 1) Discontinued before the Exit DBPCFC or did not undergo an Exit DBPCFC for any other reason
- 2) Failed the Exit DBPCFC (e.g., a subject who did not tolerate a single dose of at least 600 mg of peanut protein with at most mild symptoms is a 600 mg non-responder).

Classification as a 300 mg non-responder and a 1000 mg non-responder are defined similarly.

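### Three protocol sections disagree on whether repeated missed dosing in Maintenance stops a subject, so access to the Exit DBPCFC and responder status depend on which section a site follows.

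*Protocol*

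**What the plan says.** **Protocol 6.8** counts excessive missed dosing as "3 consecutive days of missed doses on 3 occasions during the Up-dosing Period or on 3 occasions during the Maintenance Period". Lapses that were part of treating an adverse event are exempt. It says that meeting this criterion "constitutes an individual stopping rule and the subject is to stop taking study product", and adds: "The subject will be considered an escalation failure nonresponder". The section heading nevertheless refers only to missed doses during Up-dosing.

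**Protocol 4.3.1** lists non-adherence among the reasons for which a subject may be terminated from further allergen exposure. The repeated-lapse part reads "3 consecutive days on 3 or more occasions during the Up-dosing Period, as this could constitute a potential safety issue". Maintenance is not mentioned, and the wording is permissive.

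**Protocol 7.10.2** calls a significant number of missed-dosing episodes an individual stopping rule and describes it as "ie, 3 or more consecutive days on at least 3 occasions) during the Up-dosing Period". Again Maintenance is not mentioned.

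**Protocol 6.3.5** requires 300 mg/d for at least the last 2 consecutive weeks of Maintenance to qualify for the Exit DBPCFC. It sets no limit on earlier repeated lapses.

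**SAP 7.4.1 and 7.4.2** classify by the Exit DBPCFC: a responder is a subject who tolerates the dose with at most mild symptoms. The first non-responder condition is "Discontinued before the Exit DBPCFC or did not undergo an Exit DBPCFC for any other reason". SAP Table 7.1 labels subjects who had no Exit DBPCFC by the period of their last dose.

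**The concern.** The three sections differ in the period covered (6.8 includes Maintenance; 4.3.1 and 7.10.2 do not) and in force (mandatory in 6.8 and 7.10.2, optional in 4.3.1). For lapses in Maintenance this decides whether dosing stops, whether there is an Exit DBPCFC and, through that, the subject's status on the primary endpoint. Because 6.8 is headed as an Up-dosing section, a site handling a Maintenance lapse may not look there.

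Two things are at stake. One is uniform handling across sites of a criterion that 4.3.1 itself ties to safety. The other is a primary endpoint whose value for some children depends on which section the site read.

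**Working it through.** **Step 1. The rules side by side, for lapses in Maintenance**

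| Section | Covers Maintenance? | Force | Consequence for repeated lapses |
|---|---|---|---|
| Protocol 6.8 | Yes | Mandatory | Stop; escalation failure nonresponder |
| Protocol 4.3.1 | No, Up-dosing only | Optional | Criterion not met |
| Protocol 7.10.2 | No, Up-dosing only | Stopping rule | Criterion not met |
| Protocol 6.3.5 | Yes | Exit DBPCFC eligibility | Looks only at the last 2 weeks |

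**Step 2. One child, two outcomes**

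Take a child with three separate 3-day lapses in Maintenance, none for adverse-event treatment, who is on 300 mg/d for the last 2 weeks. After a 3-day lapse, 6.8 resumes dosing at the current dose under supervision, so returning to 300 mg/d is the expected course after the first two lapses.

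- Under 6.8, the third lapse stops dosing. There is no Exit DBPCFC and the child is a nonresponder.
- Under 4.3.1 or 7.10.2, no repeated-lapse rule is met. The child qualifies under 6.3.5, takes the challenge and, on tolerating 600 mg (North America) or 1000 mg (Europe), is a responder under SAP 7.4.1.

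**Step 3. Does the SAP contradict 6.8?**

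Not for a subject who is stopped. With no Exit DBPCFC, that subject is a non-responder under SAP 7.4.2 and 7.6 and a treatment failure under Protocol 9.2.1.

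**Step 4. The label**

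Protocol 3.2 starts Maintenance at the first home dose of 300 mg. Anyone stopped for Maintenance lapses has therefore taken such a dose, and SAP Table 7.1 calls that subject an OIT Maintenance Failure. Protocol 6.8 calls the same subject an escalation failure. This affects the subcategory tables, not the primary endpoint.

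**Step 5. Scale**

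Inputs: 495 children randomized 3:1, with planning rates of 50% versus 20% (North America, margin 0.15) and 30% versus 15% (Europe), all from Protocol 9.4. AR101 children: 495 × 0.75 = 371; placebo: 124. The share affected, f, is not in the documents; 2% to 5% is an assumption.

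- Children affected on AR101: 0.02 × 371 = 7; 0.05 × 371 = 19. Each reclassified child moves the rate by 1/371 = 0.27 points.
- Not all would pass the challenge. With half would-be responders, the AR101 rate moves 0.50 × f = 1.0 to 2.5 points.
- The placebo rate moves 0.20 × f = 0.4 to 1.0 points if affected equally.
- The North America difference moves 0.30 × f = 0.6 to 1.5 points out of 30. The Europe difference moves 0.15 × f = 0.3 to 0.75 points out of 15.

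Power for the Farrington-Manning test is Φ[(p1 − p2 − margin − 1.96·s0)/s1]. Here s0 is the standard error under the restricted null estimates and s1 the standard error at the planning rates.

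- Plan's own figures: North America (0.15 − 1.96 × 0.0489)/0.0443 = 1.22, or 88.9% (stated about 89%). Europe gives 93.5% (stated at least 93%). Both reproduce.
- f = 2% in both arms: North America (0.144 − 1.96 × 0.0486)/0.0441 = 1.11, or 86.6%; Europe 92.9%.
- f = 5% in both arms: North America (0.135 − 1.96 × 0.0481)/0.0437 = 0.93, or 82.4%; Europe 91.8%.

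These compare all affected children being stopped with none being stopped, taking the planning rates as the rates with none stopped. The documents do not say whether the 50% assumption already allows for such stops.

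**The case against.** The best defence is that the sections can be read together. Section 6.8 is the detailed missed-dose section; 4.3.1 and 7.10.2 are short lists that are silent on Maintenance and do not say that a subject with Maintenance lapses may continue. A site can follow 6.8 without breaching either. Section 3.3 also reserves the Exit DBPCFC for subjects who maintain 300 mg through Maintenance, and 9.2.1 counts failure to maintain the daily dose as treatment failure.

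This stands in part: a site that reads 6.8 has a clear instruction. But two places that state the criterion name one period, a third names two, and 6.8's own heading names one. Neither 3.3 nor 9.2.1 says how many missed days amount to failing to maintain the dose, while the specific eligibility text in 6.3.5 looks only at the last 2 weeks. The text of 7.10.2 is damaged just after the quoted phrase, so nothing here rests on its cross-reference.

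A reader might also infer that the SAP conflicts with 6.8 and needs a rule turning a passed challenge into a failure when the missed-dose criterion had been met. The documents do not support that. A subject stopped under 6.8 is already a non-responder in the SAP. One who met 6.8 but was challenged anyway is a deviation, and the SAP has a route for it: study drug compliance is a deviation category, reviewed blind, that can remove the subject from the Per Protocol population. Keeping an observed challenge result in the ITT analysis is a defensible choice. Table 7.1 cannot hold such a subject, since it covers only those without an Exit DBPCFC.

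Finally, a reader might put the effect at 2 to 5 points. That would require every affected child to be a would-be responder.

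**Conclusion.** The inconsistency is real and lies within the protocol. For lapses in Maintenance, 6.8 gives a mandatory stop and nonresponder status, while 4.3.1 and 7.10.2 give no repeated-lapse rule. The SAP follows whatever the site did and does not create the split. The failure label also differs between 6.8 and SAP Table 7.1.

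The size cannot be derived from the documents. On the assumed 2% to 5%, with the planned 50% response among those affected, the AR101 rate moves about 1 to 2.5 points and the North America difference about 0.6 to 1.5 points. Both figures suppose that all of these children, and not just some, are handled one way and not the other, so they are upper figures for that range. The effect is modest. The case for acting rests mainly on consistent conduct of a rule that bears on safety and on the primary endpoint.

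**What to change.** Reconcile Protocol 4.3.1, 6.8 (including its heading) and 7.10.2 so that the repeated-lapse criterion covers the same periods with the same force. Which periods and which force is the sponsor's clinical decision; no view is taken here. If Maintenance lapses remain a stopping criterion, change the label in 6.8 for those subjects to match SAP Table 7.1.

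No new SAP rule is needed, and an observed Exit DBPCFC result should not be overridden. A late adherence-based responder rule would be hard to defend: enrollment is complete, SAP Version 2 was written after several subjects had been individually unblinded, and SAP 10.1 reports data collection problems with the electronic diary.

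The cost is a protocol clarification and a note to sites, with no change to the analysis. It cannot alter how subjects who have already exited were handled. A blinded count before database lock of subjects meeting the Maintenance criterion, and of how each was handled, is optional; it would replace the assumed 2% to 5%, within the limits of the diary data.

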6.9 Skin Prick Test

Subjects will have skin prick tests performed using investigational site- and sponsor-approved procedures for food allergens. Detailed instructions for performance of the SPT will be provided in a manual of operating procedures. In brief, while the subject is off antihistamines for an appropriate length of time (5 half-lives of the antihistamine that is being used), a skin test probe is pressed through a commercial peanut allergen extract into the epidermis. Positive (histamine) and negative (saline-glycerin) controls are placed to establish that the response is not blocked and to determine if there is dermatographism, respectively.

6.10 Assessment of Asthma Control Using the Asthma Control Test Questionnaire

Subject or subject and parental assessment of asthma control will be performed at the specified visits using the Asthma Control Test questionnaire for subjects with asthma.

6.11 Visit Windows

Dosing schedule should be adhered to strictly. Two days before, or 2 days after a planned dosing visit, is an acceptable window with continued daily dosing of the current dose level. Study visits for scheduled blood draws or DBPCFC should take place within 2 weeks of the scheduled visit.

Early Discontinuations Visits are to occur 14 days after the last dose of study product. The permissible window is minus 3 days to plus 7 days.

6.12 Study Blinding Procedures

This is a double-blind study. The study as a whole will not be unblinded until after the last subject exits ARC003 and the database is locked.

After undergoing the Exit DBPCFC, most subjects will, however, become de facto unblinded to their on-study treatment assignment on the basis of their experience with the food challenge; ie, subjects who fail 1 part of the Exit DBPCFC early on may reasonably deduce that they had been in the placebo arm of the study, and those who tolerate both parts of the Exit DBPCFC (or fail

1 part only at the highest dose levels tested) may reasonably deduce that they had been in the AR101 arm. Hence, the study is double-blinded on an individual subject basis only up to completion of the Exit DBPCFC. It is for this reason that assessment of reactions to DBPCFC will be made by a Blinded Evaluating Physician (Blinded Assessor).

Although the unblinding of subjects after completion of the Exit DBPCFC cannot influence the manner in which they are assessed or treated by the investigational site personnel (as their participation in ARC003 will have concluded at that time), knowledge of subjects' treatment assignments could potentially influence the investigational site personnel's conduct toward other subjects who have not yet reached the conclusion of the study. The risk of bias being introduced into the determination of DLSs during DBPCFCs due to knowledge of the treatment assignments of other subjects will be substantially reduced by having the assessment of the DBPCFC results made by a Blinded Evaluating Physician (Blinded Assessor) who is not otherwise directly involved with the treatment of the subjects he or she is evaluating. Additionally, the duration of the study and the anticipated rate of recruitment are such that that enrollment should not be influenced by the Exit DBPCFC, as enrollment should be completed before the first subjects exits the study.

Additionally, to ensure that allocation of subjects to their appropriate analysis populations is not biased by knowledge of their treatment assignments, specific masking procedures have been put in place to shield study team members who could be involved in determining allocation of the subjects to the analysis populations from knowing subject treatment assignments (refer to Masking Plan). To further ensure that allocation of subjects to their appropriate analysis populations is performed in an unbiased way, subjects will not be informed of their on-study treatment assignments or rollover into the open-label follow-on study, ARC004, until all major data queries, ie queries that could influence allocation to 1 or another analysis population, have been resolved (as detailed in the Masking Plan), regulatory and IRB/EC approval for ARC004 have been received, and IP for ARC004 is available.

Those subjects who are not eligible for the DBPCFC at Week 68 of their projected up-dosing schedule, may be unblinded at this time (their projected study Week 68) or when the last subject completes the Exit DBPCFC, provided all major data queries for the subject have been resolved.

6.12.1 Securing Blinding and Randomization Information

Aimmune or one or more of its contractors will manufacture, package, label, store, and distribute the study products. During site visits, the site monitor will check the clinic and/or pharmacy logs to ensure that appropriate randomization assignments are received, recorded, and maintained.

6.12.2 Requirements for an Unblinding

Prior to the Exit DBPCFC assessment, a subject can be unblinded only when needed for making medical decisions regarding the care of a subject. The decision to unblind should, if at all possible, be made in collaboration with the sponsor's Medical Monitor. If a life-threatening event occurs, the subject should be treated as if the subject received active study product. For all unscheduled non-life-threatening events that require unblinding, the investigator will contact the clinical monitor who will coordinate with the sponsor's representatives.

6.12.3 Breaking the Blind

Site personnel or other study team members (such as a Medical Monitor) may request emergency unblinding as described above. If it is specifically necessary to provide a treatment assignment to the Sponsor, this information will be provided to a Medical Monitor and/or Clinical Operations Designee.

In case emergency unblinding is necessary, the interactive response system allows study personnel with appropriate permissions to request unblinding for a specific subject. An automated notification is then sent to the sponsor and the sponsor's safety designees to inform them of the unblinding. A built-in audit trail documents the unblinding process and the persons involved.

6.12.4 Documenting and Unblinding

Any premature unblinding requires a full written account by the site study physician of the event(s) that necessitated unblinding of the study medication for an individual participant. This account includes the reason(s) for unblinding, the name of the sponsor's medical monitor who was notified of the unblinding, the names of the unblinded individual staff members and the date and time the unblinding occurred. The treatment assignment is confidential and should not be provided to blinded team members, as detailed in the Masking Plan.

